#### 4 Participant randomization

Participants will be randomized into 2 study arms, with 50% of participants allocated to each arm:

- Study Arm 1: Control group (n = 25)
- Study Arm 2: My-AHA intervention group (n = 25)

Randomization will occur at each study site independently.

Initial randomization of participants at each site will occur on a 1 (control) : 1 (intervention) ratio, with allocation of participants to each treatment arm being undertaken using an alternating allocation sequence based on order of entry into the study (i.e. participant 1 – study arm 1; participant 2 – study arm 2; participant 3 – study arm 1; participant 4 – study arm 2, and so on).

Once recruitment and allocation to study arms of 20 participants has occurred at each site. The study site PI will submit to the RCT Study Coordinator basic demographic information on the 20 participants recruited and allocated to study arms. The demographic information required for each of the 20 participants is:

- Gender
- Age
- Highest education level

The RCT study coordinator will review the balance of participants across study arms for these demographic variables within each study site and advise the Principal Investigator of any adjustment to the allocation procedures for remaining participant assignment to treatment arms to ensure equivalence of study arms within each site.

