## 1 Protocol Flowchart

**Figure 1: Protocol flowchart**

The My-AHA RCT protocol comprises 6 elements that will be described in detail below:

1. Participant recruitment
2. Participant screening
3. Randomised allocation to control or intervention arm
4. Periodic assessments
5. Interventions
6. My-AHA User Platform interface

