## 2 Recruitment

### 2.1 Type and Number of Participants

Participants will be adults aged 60 years and older meeting study inclusion criteria for pre-frailty (Table 2) and not meeting study exclusion criteria for clinically significant cognitive and/or mood disturbance (Table 4) or for concomitant diseases (see Section 3.2).

A total of 50 participants will be recruited from the Sunshine Coast region. Participants will be community residing older adults, residing either in their own home/unit, retirement community, or residential aged care (non-secure). The majority are likely to be living in a semi-supported independent living setting receiving some aged care support services in own home/residence but otherwise fully independent.

Participants who volunteer to participate in the RCT must be screened to ensure that each participant meet all inclusion criteria (Table 1) and do not meet any exclusion criteria (Table 3).

---

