### 3.3 Screening Failures

Screen Failures are defined as participants who sign a Screening Participant Informed Consent Form (PICF-Screen) for My-AHA study but are not subsequently randomized and who do not enter the RCT. Participants who are Screen Failures may be rescreened once only after approval by the study Medical Supervisor (University of Torino, Italy).

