## 7 My-AHA Interventions

The intervention in this study is defined as the My-AHA platform. Participants randomized into the intervention arm will have access to the full My-AHA intervention platform (see also Section 8 My-AHA User Platform interface). Participants in the control group will not have access to the intervention package (no treatment control). All participants recruited into the study have no active disease state being treated. All participants meet study criteria for pre-frail status, a non-clinical disease state.

The protocol in the intervention arm is designed to prevent deterioration from a non-clinical state (pre-frail) into the disease state (frail).

The no-intervention control arm will not receive any element of the My-AHA intervention, a no-intervention non-disease control group. Participants in both study arms undergo formal assessment of clinical frailty status at 4 timepoints (baseline, 6 mo, 12 mo, 18mo). **Development of clinical frailty is considered an adverse endpoint for the participant in this study.**

Where a control group participant displays evidence of clinical decline at 6 or 12mo assessment points (defined as meeting clinical criteria for frailty) they will be offered access to the My-AHA intervention suite. We cannot estimate or predict what proportion of the control participants may develop frailty during the 18 month trial as there is no published data on incidence, age-dependent prevalence, or on average rate of decline into frailty from pre-frail states.

Participants randomly allocated to the intervention group will be provided with access to tailored intervention packages. Intervention packages will target domains of pre-frailty (e.g. physical, social, cognitive, nutrition) identified at baseline assessment for each participant. The intervention packages will be revised following each assessment point to accommodate for changes in domain specific areas of pre-frailty.

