### 10.2 Project wide

The study coordinator is responsible for the management and storage of multi-site de-identified data collected across the multiple sites involved in the RCT.

1. Data from each participant will only be identified by a unique identifier code indicating the study site from which the data was collected
2. No persons will be able to identify the identity of the individual from the identifier code used. Only the site PI will retain the master key for participant identities specific to their site.
3. Data storage and security of the combined multi-site data is the responsibility of the study coordinator

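### Allocation is called randomised, but Section 4 prescribes strict alternation by order of entry, so at least the first 20 assignments at each site are known in advance

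*Protocol*

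**What the plan says.** The protocol describes the allocation as random in several places. The list of protocol elements in Section 1 includes "Randomised allocation to control or intervention arm". Section 7 refers to "Participants randomly allocated to the intervention group". Section 4 is titled as randomisation and gives a 1:1 split, 25 per arm, run separately at each site.

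The mechanism in Section 4 is different: "allocation of participants to each treatment arm being undertaken using an alternating allocation sequence based on order of entry into the study". The sequence is spelled out, with odd entry numbers going to control and even entry numbers to intervention.

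Once a site has allocated 20 participants, the RCT Study Coordinator reviews gender, age and education by arm and will then "advise the Principal Investigator of any adjustment to the allocation procedures for remaining participant assignment to treatment arms". No rule or random element is given for that adjustment.

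On size, Section 2.1 says "A total of 50 participants will be recruited from the Sunshine Coast region", while Section 10.2 speaks of "multi-site de-identified data collected across the multiple sites involved in the RCT". The multi-site total is not stated.

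**The concern.** Alternation contains no chance element. Because the starting arm is fixed as well, even the first assignment is known. The control group receives no treatment and no masking is described, so earlier assignments are visible to site staff and the next one follows from the count.

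The person enrolling can therefore decide who takes the next slot. Numeric eligibility cut-offs and the rescreening limit ("Participants who are Screen Failures may be rescreened once only after approval by the study Medical Supervisor") restrict who may enter. They do not restrict when an eligible person is entered, and order of entry is exactly what sets the arm. Section 3.3 itself treats screening and entry into the RCT as separate steps, so screening order does not fix the slot.

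At stake is the basis for attributing a difference between arms to the intervention. Selection on characteristics nobody recorded cannot be repaired in the analysis, and balance on three demographic variables does not rule it out.

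**Working it through.** **1. The plan's own figures.** Applying the printed rule (odd = control, even = intervention) gives 10/10 after 20 participants and 25/25 after 50. The stated arm sizes are reproduced. The numbers are right; the mechanism is the problem.

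**2. Predictability, from the protocol alone.** I treat the Sunshine Coast as one site, which the protocol does not say outright.

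| Situation | Assignments known in advance |
|---|---|
| First 20 at a site | 20 of 20 |
| Whole site of 50, any outcome of the review | at least 20 of 50 = 40% |
| Whole site of 50, no adjustment advised | 50 of 50 = 100% |

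If the region were split into several sites, the known share would rise. Two sites of 25, for example, would give 20 + 20 = 40 of 50.

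For comparison, a guesser is right 50% of the time under simple 1:1 randomisation. With permuted blocks whose fixed size is known, the figure is 75.0% (size 2), 70.8% (size 4), 68.3% (size 6) or 66.6% (size 8).

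**3. Illustration of the bias. Every input here is assumed.** One site of 50 (25:25), no true effect, continuous outcome, t-test at two-sided 0.05. In a share p of the steerable slots the recruiter has two candidates and enters the better one into intervention or the worse one into control. Prognosis correlates ρ with outcome.

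The expected maximum of two standard normal values is 1/√π = 0.564 and the expected minimum is −0.564. The spurious difference in SD units is therefore

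2 × p × ρ / √π × (steerable slots / 50).

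- Lowest case (p = 0.25, ρ = 0.3): 2 × 0.25 × 0.3 / 1.772 = 0.085 for 50 slots; × 20/50 = 0.034 for 20 slots.
- Highest case (p = 0.5, ρ = 0.5): 2 × 0.5 × 0.5 / 1.772 = 0.282 for 50 slots; × 20/50 = 0.113 for 20 slots.

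Rejection rates come from 100,000 simulated trials per cell:

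| p, ρ | 20 slots: difference | 20 slots: type I error | 50 slots: difference | 50 slots: type I error |
|---|---|---|---|---|
| 0.25, 0.3 | 0.034 | 5.1% | 0.085 | 6.0% |
| 0.25, 0.5 | 0.056 | 5.5% | 0.141 | 7.9% |
| 0.5, 0.3 | 0.068 | 5.6% | 0.169 | 9.0% |
| 0.5, 0.5 | 0.113 | 6.6% | 0.282 | 16.8% |

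With no steering the rejection rate was 4.9 to 5.0%, as it should be.

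**4. Sensitivity to the model.** The table assumes the passed-over candidate never enters. If that person instead waits and is entered later, which is closer to steering by timing, the p = 0.5, ρ = 0.5 case gives 0.18 and 9.3% for 20 slots, and 0.44 and 34% for 50 slots. The table is therefore on the low side for the mechanism that matters here.

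**The case against.** The strongest reply leaves the core contradiction alone and attacks the size.

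- **All steering inputs are assumed.** The protocol gives no recruitment rate or queue length, and nothing shows that two candidates would ever wait together. The one adverse endpoint named in Section 7, becoming frail, is yes/no, whereas the illustration uses a continuous outcome. This stands. The figures show plausibility and are not an estimate.
- **Direction is not fixed.** A recruiter might give intervention slots to people seen as needier, which would bias against the intervention. This also stands; the concern is bias either way.
- **The review after 20 could expose steering on gender, age or education.** That is partly right, so the all-50 figures are an upper scenario. But three variables in 20 people form a weak check, and unrecorded prognosis is untouched.
- **Any concealed random sequence would cure the defect.** True. Block details and the choice of minimisation are matters of good practice beyond the minimum.

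A separate analysis plan would not help. The allocation rule is fixed in the protocol, and no analysis makes an alternated sequence random or concealed.

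**Conclusion.** The concern holds and should be fixed before further participants are allocated. Section 4 prescribes a deterministic, unconcealed sequence and calls it randomisation, and nothing elsewhere in the protocol supplies a random element.

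The firm part of the size comes from the text: every one of the first 20 assignments per site is known in advance, and all of a site's assignments are known if no adjustment is advised. The illustrative bias ranges from negligible (type I error 5.1%) to serious (16.8%, or 34% if passed-over candidates are entered later). It rests wholly on the assumed steering frequency, prognostic correlation and number of steerable slots. No trial-wide figure can be given because the multi-site total is not stated.

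One question is left open. The contents list names separate RCT consent forms for the two arms, and Table 6 places consent at both screening and baseline. The protocol should say whether the arm is known before RCT consent and baseline testing. The consent text was not available, so this is not counted as a fault.

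**What to change.** Amend Section 4 as follows.

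1. Replace alternation with a computer-generated sequence, stratified by site, in permuted blocks of randomly varying, undisclosed size. If balance on gender, age and education is wanted, use instead minimisation on those three factors with a random element from the first participant.
2. Have the existing RCT Study Coordinator hold the sequence centrally and release each assignment only after eligibility, RCT consent and baseline assessment are complete.
3. Delete the discretionary adjustment after 20 participants.
4. If recruitment has begun, apply the new procedure to everyone not yet allocated. Flag those already alternated, report them as alternated and not randomised, and repeat the main comparison without them. If 20 of 50 were alternated, that repeat would have only 50 − 20 = 30 participants, so it would be imprecise.

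The cost is one protocol amendment and one list per site, or one minimisation program. Sites lose manual control, the coordinator must answer each allocation request, and the arms may differ slightly from 25:25. No extra participants or staff are needed.

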**Table 2: Pre-frail inclusion criteria for participant screening**

Clinical sign/symptom	Measure	Cutoff values			
PHYSICAL DOMAIN					
Pre-frail = 1 or 2 of the following criteria are met					
1. Shrinking, evidenced by weight loss (unintentional)	$\geq 4.5$ kg unintentional in prior 12 months; or at follow-up assessment $\geq 5\%$ of body weight in prior 12 months	Self-reported weight loss (not due to dieting or fasting) in preceding 12 mo $\geq 4.5$ kg Follow-up: $K = (\text{weight in previous year} - \text{current measured weight}) / (\text{weight in previous year})$ . If $K \geq 0.05$ , meets weight loss frailty criteria			
2. Weakness	Grip strength in lowest 20% at baseline adjusted for gender and BMI	BMI Men BMI $\leq 24$ Men BMI 24.1 - 26 Men BMI 26.1 - 28 Men BMI $> 28$  Women BMI $\leq 23$ Women BMI 23.1 - 26 Women BMI 26.1 - 29 Women BMI $> 29$	Grip strength cutoff (kg) $\leq 29$ $\leq 30$ $\leq 30$ $\leq 32$  $\leq 17$ $\leq 17.3$ $\leq 18$ $\leq 21$		
3. Poor endurance and energy	Self-report of exhaustion as indicated by responses to 2 questions on CES-D scale	Using the CES-D Depression Scale, response of “2” (a moderate amount of the time, 3-4 days) or “3” (most of the time) to either of the following 2 items: (a) I felt that everything I did was an effort; and/or (b) I could not get going.			
4. Slowness	Time to walk 15ft (4.57m) $\leq$ slowest 20% adjusted for gender and standing height	Gender/Height (cm) Men Height $\leq 173$ cm Men Height $> 173$ cm Women Height $\leq 159$ cm Women Height $> 159$ cm	Cutoff time to walk 4.00 m) $\geq 6.13$ sec $\geq 5.25$ sec $\geq 6.13$ sec $\geq 5.25$ sec		

5. Low physical activity level	Energy expenditure per week below established cutoff	Short version of the IPAQ questionnaire assesses activity levels for walking, moderate-intensity and vigorous-intensity activities for work, transportation, domestic chores, gardening and leisure-related activities.	IPAQ Activity level measures as MET-min units). Convert IPAQ Met-min units to kcal using following formula adjusting for participants weight in kg: $[\text{kcal} = \text{MET-min} \times (\text{weight kg}/60)]$ Gender specific cutoff values: 
 
▪ Men: < 383 kcal
 
▪ Women: <270 kcal
 

---------------------------------------	--	---	--

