## 6.4 Demographic measures

### 6.4.1 Standard demographic questionnaire

At baseline assessment, all participants will be required to complete the *Standard Demographic Questionnaire* (Appendix 5).

This questionnaire collects information from each participant regarding:

- Date of birth
- Gender
- Education (years completed)
- Residential status (live alone, with other etc.)
- Fear of falls
- Falls history
- Cognitive activities (mental activity)
- Medical history (diseases/diagnoses past and current, medication history)
- Continence/incontinence

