## My-AHA Demographic Questionnaire - BASELINE

### Demographic Information

Date of birth : DD / MM / YYYY

Age (years): \_\_\_\_\_

Gender: Male / Female *(circle one)*

Handedness Right / Left *(circle hand you write with)*

Height \_\_\_\_\_ cm

Weight \_\_\_\_\_ kg

Marital Status: Single / Married / Defacto / Widowed *(circle one)*

Describe your living situation

- Alone
- With a partner/spouse
- With children/grandchildren

Where do you live?

- Own home (house / apartment / unit)
- Residential village (e.g. retirement community)
- Supported accommodation (e.g. aged care facility)
- Nursing home

Are you currently living

- Independently with no support services
- Semi-independently – receive some support services (e.g. meals on wheels, cleaning support, etc)
- Fully dependent care (e.g. nursing home with meals and medical care provided)

Prior education history

A. \_\_\_\_\_ Total number of years at school (primary + high)

B. \_\_\_\_\_ Total number of years of post-school formal education  
(e.g. University/College)

C. \_\_\_\_\_ TOTAL EDUCATION YEARS (A+B)

Have you ever fallen over? Yes / No

If YES describe when and what occurred  
(e.g. injury) \_\_\_\_\_

\_\_\_\_\_

\_\_\_\_\_

\_\_\_\_\_

\_\_\_\_\_

How fearful are you of falling? 0 1 2 3 4 5

Never Rarely A little Moderately Often Always

Are you currently continent? Urinary Yes / No  
Bowel Yes / No

What type of events or entertainment have you undertaken in the last 2 months?  
(*tick all that apply*)

- Movies
- Plays / drama productions
- Pub / Club
- Concert / Recital
- Special Performances
- Dancing
- Visiting Friends
- Attending a sporting event
- Meal at a restaurant

How would you spend a typical day  
(*tick all that apply*)

- Sleep / nothing
- House work
- TV
- Radio
- Listening to music
- Walking
- Gardening
- Crosswords
- Pet care
- Socialising
- Reading
- Writing
- Studying
- Teaching
- Volunteering
- Paid work
- Strategy games (e.g. chess, bridge, cards)
- Helping friends/family
- Artistry (e.g. drawing, painting, sculpture, creative writing, acting, etc.)
- Prayer / religious activity
- Playing music
- Brain training games (on a computer, ipad etc)
- Learning something new
- Hobby or past-time
- Intellectual/professional

How often do you make an outing to see a family member,  
friend or a group of friends?

- Never
- Less than monthly
- Monthly
- Fortnightly
- Weekly
- Daily

Are you currently diagnosed with a medical condition? Yes / No

IF YES

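### The arm-balance review after 20 participants leaves out the number of pre-frailty criteria met at screening (1 or 2), the recorded baseline variable closest to the frailty endpoint

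*Protocol*

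**What the plan says.** Section 4 allocates participants 1:1, "with 50% of participants allocated to each arm", and gives 25 per arm. Section 2.1 gives the total: "A total of 50 participants will be recruited from the Sunshine Coast region". Once a site has allocated 20 people, it sends three items on each of them to the study coordinator: gender, age and "Highest education level". Then "The RCT study coordinator will review the balance of participants across study arms for these demographic variables within each study site", and the coordinator may advise changing how the remaining participants are allocated. The stated aim is that the arms be equivalent within each site.

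Eligibility rests on a count of physical criteria. Table 2 states: "Pre-frail = 1 or 2 of the following criteria are met". The Appendix 4 checklist totals the count out of five and excludes anyone with none or with more than two. Section 7 ties the trial's purpose to that scale: "Development of clinical frailty is considered an adverse endpoint for the participant in this study".

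On education, Section 6.4.1 lists "Education (years completed" as the unit of collection. The Appendix 5 baseline form records years at school, years after school and their sum, under "TOTAL EDUCATION YEARS (A+B".

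**The concern.** The review can change allocation, so its list of variables matters, and a later analysis plan cannot alter how people were allocated. All three variables are demographic and none measures frailty. Yet the eligible population consists of two groups at different distances from the endpoint. If frail means more than two criteria, a person entering with 2 is one criterion away and a person entering with 1 is two away. At 25 per arm the mix of the two groups can differ noticeably by chance, and the review as written would not show it.

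A reader of the results would ask about this mix first. It also affects how many controls are expected to reach frailty at 6 or 12 months, and Section 7 gives those controls access to intervention content.

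A smaller mismatch sits in the same list. Highest education level is not an item on the screening checklist or the baseline demographic form. The only form that asks for it is the DART questionnaire (Appendix 26), which is worded for people who have used the app for some months. That is too late to inform allocation.

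**Working it through.** **The plan's own figure.** 50 × 0.5 = 25 per arm, which agrees with Section 4. The protocol gives no other figure on this point to reproduce.

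**Review list against what is recorded**

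| Variable | In the Section 4 review? | Recorded before allocation or at baseline? |
|---|---|---|
| Gender | yes | yes (Appendices 4 and 5) |
| Age | yes | yes (Appendices 4 and 5) |
| Highest education level | yes | no; years only (Appendix 5) |
| Number of pre-frailty criteria, 1 or 2 | no | yes (Appendix 4 total out of 5) |

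**Chance imbalance at full size.** Let K be the number of the 50 who enter with 2 criteria. The protocol gives no K, so it is assumed. Under random allocation of 25 to each arm, the number X in one arm is hypergeometric (50, K, 25). The other arm has K − X, so the gap in shares is |2X − K| / 25. A gap of 20 points is 5 people (5/25) and one of 28 points is 7 people (7/25).

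| K (assumed) | P(gap ≥ 20 points) | P(gap ≥ 28 points) |
|---|---|---|
| 10 | 0.074 | 0.011 |
| 15 | 0.217 | 0.062 |
| 20 | 0.148 | 0.042 |
| 25 | 0.258 | 0.089 |

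The figures do not rise steadily with K because 2X − K is odd or even with K. For K = 10 or 20 the smallest gap that reaches 20 points is 6 people, or 24 points.

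**At the 20-person review (10 v 10).** For two independent binomials with a share p having 2 criteria, P(gap ≥ 20 points) is 0.394 at p = 0.2, 0.463 at p = 0.3 and 0.503 at p = 0.5. A gap of this size is therefore common at the moment when the coordinator could still respond to it.

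**What a gap does to the frailty comparison.** With no treatment effect, the expected shift in the risk difference, given the gap, is gap × (risk with 2 − risk with 1). The risks below are assumed; Section 7 says that no published rates exist.

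- 5% and 20%: 0.20 × 0.15 = 3 points
- 5% and 30%: 0.20 × 0.25 = 5 points
- 10% and 40%: 0.20 × 0.30 = 6 points

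**Set against sampling error.** With K = 15 (30%), the average risk in the first case is 0.3 × 0.20 + 0.7 × 0.05 = 0.095, and the standard error of the risk difference is √(2 × 0.095 × 0.905 / 25) = 0.083. In the third case the average is 0.3 × 0.40 + 0.7 × 0.10 = 0.19, and the standard error is √(2 × 0.19 × 0.81 / 25) = 0.111. The shifts of 3 and 6 points are 0.36 and 0.54 of a standard error (0.03 / 0.083 and 0.06 / 0.111). Those standard errors already include chance variation in the mix.

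**The case against.** **A false treatment effect.** A reader might infer that an imbalance in the count turns directly into a spurious frailty difference. The documents do not support that. Under proper randomisation the imbalance averages to zero, and the usual standard error allows for it. The shifts above are conditional on an unlucky draw. What stands is lost precision and a result that is harder to defend.

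**A choice of variables.** Balancing on basic demographics contradicts nothing in the protocol, and other baseline measures could be argued for. That is fair. The count differs in that it defines eligibility, lies on the same scale as the endpoint and is already held at allocation.

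**Scope of the figures.** The 50 may be one site's sample, because Section 10 describes combining data across sites. The documents give no pooled total. If it were 100 or 200 (assumed), with 30% to 50% entering with 2 criteria, the same calculation gives about 5% to 7% and under 1%. The 15% to 26% therefore applies to a 50-person comparison. It also models random allocation, whereas Section 4 specifies alternation by order of entry. That predictability is a larger weakness, and adding a variable to the review does not cure it.

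**Analysis model.** Adjusting for the count would recover much of the lost precision, and that decision belongs to the SAP, which is not at hand. Its absence from the protocol is no fault.

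**Education.** A reader might infer that the review cannot be run on education at all. That goes too far. Section 6.7.1 gives education bands partly in years, Appendix 5 separates school from post-school years, and a site could simply ask. Only a completed qualification cannot be derived. This half is a wording mismatch.

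**Conclusion.** The point holds as a modest, inexpensive improvement to Section 4. The review aims at equivalent arms but omits the recorded baseline variable closest to the endpoint. At 25 per arm under random allocation, a gap of 20 points or more in the share entering with 2 criteria has probability of about 15% to 26% if 15 to 25 of the 50 do so, and about 7% if 10 do; pooling across sites lowers it. The consequence is reduced precision and credibility, not systematic bias.

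The conclusion rests on three things that the protocol does not state: the two-criterion share, the frailty risk by count, and frail meaning 3 or more criteria. The first two affect only the size. The third supports the claim that the count measures distance from the endpoint, and it follows naturally from the exclusion of anyone with more than two.

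**What to change.** In Section 4, add the number of pre-frailty criteria met at screening (1 or 2) to the balancing variables. Preferably make it a stratification or minimisation factor in a concealed random allocation, so that balance does not depend on a discretionary correction after 20 people. Leave adjustment for the same count in the frailty analysis to the SAP.

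In the same list, replace highest education level with total years of education as collected in Appendix 5. It would also help to state in Section 3.1 or Section 7 the number of criteria that defines frailty, since it is now only implied.

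The cost is small. The count and the years of education are already collected and no new assessment is needed. The downside is one more balancing factor, which with 50 people argues for keeping the total number of factors low.

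### After 20 participants at a site, Section 4 allows an open-ended, rule-free change to how the rest are allocated, so up to 30 of 50 could be assigned by discretion

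*Protocol*

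**What the plan says.** Protocol Section 2.1 sets the size: "A total of 50 participants will be recruited from the Sunshine Coast region". Section 4 states that "Participants will be randomized into 2 study arms, with 50% of participants allocated to each arm", which it gives as 25 control and 25 intervention, and that each site allocates on its own. The method at the start is assignment "using an alternating allocation sequence based on order of entry into the study".

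After 20 people have been allocated at a site, the site investigator sends the coordinator three items for each of them: gender, age and "Highest education level". The coordinator compares the arms on these items, separately for each site, and is to "advise the Principal Investigator of any adjustment to the allocation procedures for remaining participant assignment to treatment arms to ensure equivalence of study arms". Section 4 says nothing further about the adjustment.

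Elsewhere the trial is presented as randomised. Section 1 lists randomised allocation among the protocol's elements, and Section 7 describes intervention participants as randomly allocated. On education, the baseline questionnaire in Appendix 5 asks for school years and post-school years and adds them in the field "TOTAL EDUCATION YEARS (A+B". It has no field for highest level.

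**The concern.** The clause is a positive instruction that authorises a mid-trial change to allocation without limiting what the change may be. It names no threshold of imbalance, no algorithm, no chance element, no concealment step and no independent person to apply the result. The person told of the new procedure is the investigator at the site that recruits.

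Three things are at stake:

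- **Selection.** Appendix 4 has an investigator count the physical frailty criteria at screening, with one or two needed for entry. A plausible prognostic marker is therefore known at the site before assignment. Section 7 gives controls no treatment, so a site could have reason to prefer one arm for a particular person.
- **Description.** Assignment by judgement after looking at the arms is not randomisation.
- **The stated aim.** Steering on gender, age and education cannot make the arms equivalent on factors outside that list, such as the number of frailty criteria met, grip strength or gait speed.

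This is separate from the alternating sequence. If the first 20 were properly randomised, the clause would still apply to everyone after them. Nor is it a detail that could wait for a statistical analysis plan, because allocation has to be fixed before the first assignment.

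**Working it through.** **Inputs from the protocol.** Total 50 (Section 2.1); 1:1 ratio, 25 per arm, alternation, and review after 20 at each site (Section 4). The protocol gives no alpha, power, effect size or standard deviation that bears on this point.

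**1. The plan's own figures.** 50 × 0.5 = 25 per arm. Alternation puts 20/2 = 10 of the first 20 in each arm, so 25 − 10 = 15 more are needed in each. These agree with Section 4.

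**2. Share exposed to the clause.** With one site, 50 − 20 = 30, and 30/50 = 60%. If the 50 were split over two sites of 25, it would be 2 × (25 − 20) = 10, and 10/50 = 20%. Only one region is named for the 50, so one site is the natural reading. Both figures are ceilings, since the coordinator may advise no change.

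**3. Would the review tend to show something to adjust?** (Assumption: three independent, roughly normal covariates and no true difference.) At 10 against 10 the standardised mean difference has standard error √(2/10) = 0.447.

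- For a difference above 0.25: 0.25/0.447 = 0.559, two-sided probability 0.58 for one covariate. For at least one of three: 1 − (1 − 0.576)³ = 0.92.
- For a difference above 0.5: 0.26 for one covariate and 0.60 for at least one of three.
- For gender, an exact binomial calculation gives counts differing by two or more in 46% to 50% of cases when one gender makes up 50% to 70% of participants.

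Some imbalance will therefore usually be visible by chance. With no threshold, whether to act on it is a matter of judgement.

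**4. What discretion over the 30 could do.** (Assumptions: standard normal outcome, no treatment effect, 20,000 simulated trials per row.) The first 20 alternate. The other 30 are ranked on an impression with correlation ρ to the outcome; the upper 15 go to one arm and the lower 15 to the other. The analysis is a two-sided 5% t-test, 25 against 25.

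| ρ | Mean between-arm difference (SD) | Rejection of a true null |
|---|---|---|
| 0 | 0.00 | 5% |
| 0.1 | 0.09 | 6% |
| 0.2 | 0.19 | 10% |
| 0.3 | 0.28 | 16% |
| 0.5 | 0.46 | 37% |

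As a check, the difference should be proportional to ρ. At ρ = 1 the simulation gave 0.933, and 0.3 × 0.933 = 0.28 and 0.5 × 0.933 = 0.47, in line with the table. Every row keeps exactly 25 per arm, so equal arm sizes give no protection.

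**5. The education item.** Section 4 asks for the highest level reached; Appendix 5 records years. Section 6.7.1 corrects the MMSE for level of education, so a level is needed for scoring, but neither the screening checklist in Appendix 4 nor Appendix 5 has a field for it. The DART questionnaire (Appendix 26) does ask for it, but that form looks back on months of app use and so follows allocation.

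**The case against.** The strongest reply is that this is a balance check on three harmless demographic items, done by someone away from the site. The coordinator advises and may advise nothing, and Section 10.1 has data reach the coordinator de-identified. Nothing suggests that the coordinator sees outcomes or knows the participants. That stands. It means that 30 is a ceiling, and that the clause permits steering without showing that anyone intends it. It does not supply the missing rule, and the adjusted procedure still goes to the site.

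A second reply is that the simulation does not isolate this clause. It splits all 30 on an impression of prognosis, in one direction, whereas the review concerns gender, age and education; alternation is also open to selection by order of entry. This stands too. The table shows what unconstrained discretion could do over a range of assumptions. It does not forecast this trial, and at ρ = 0 there is no inflation.

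Some stronger readings are tempting but not supported:

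- **That the investigator who receives the advice also measures outcomes.** The protocol does not say so. Section 6.7.1 gives the MMSE to a trained researcher, and Section 6.6 refers to an examiner.
- **That the 25/25 split will be lost.** Section 4 fixes 25 per arm, and an adjustment can respect that.
- **That this clause is what removes the randomisation basis for p-values.** Deterministic alternation already lacks one.
- **That education level is used nowhere before follow-up.** The MMSE correction uses it, and it can be approximated from years. The mismatch of forms is minor.
- **That a single shift in frailty risk can be quoted.** Section 7 says the proportion who will become frail cannot be predicted, so any such figure would rest on risks the protocol does not contain.

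**Conclusion.** The concern holds in limited form. Section 4 allows the allocation of everyone after the first 20 at a site to be changed at discretion, after the arms have been compared, by a procedure that the recruiting site will know. On the one-site reading this reaches up to 30 of 50 participants (60%); with two sites of 25 it would be 20%. The clause permits selection bias, does not fit the description of the trial as randomised, and cannot deliver the equivalence it promises beyond three demographic variables.

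The size of any bias is not fixed by the documents. Under the assumptions shown, the rejection rate of a nominal 5% test under the null runs from 5% (impression unrelated to outcome) to 37% (correlation 0.5). Covariate adjustment afterwards cannot repair selection on factors that nobody recorded, so the change is needed before enrolment.

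**What to change.** Delete the mid-course adjustment from Section 4 and replace the alternating sequence in the same edit. Deletion alone would leave the remaining 30 on a predictable sequence.

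Specify, before the first participant, one of the following:

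- a concealed, computer-generated list stratified on the chosen factors, with few strata, since three factors at two levels already make 2 × 2 × 2 = 8 strata of about 6 people each (50/8); or
- minimisation with a random element on gender, age and years of education.

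The list or program should be held by the coordinator or another existing person who neither recruits nor assesses, and each assignment released only after the participant is enrolled. Name years of education, as Appendix 5 collects it, in place of highest level. Because the Appendix 4 checklist has no education item, the years must be recorded before assignment. Handle remaining imbalance by pre-specified covariate adjustment.

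The cost is a rewritten passage in Section 4, one item moved earlier, and a pre-generated list or small program. No extra participants or staff are needed.
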